**NCT number: 20210712**

**Date: 2020/08/17**

## **Study Protocol and Statistical Analysis Plan**

### ***Study population***

The program of “Two Cancer (breast and cervical cancer) Screening” has been launched in China since 2009 to provide free screening tests for millions of rural women aged 35-59 years (Ministry of Health of China and All-China Women’s Federation). This program has been expanded to all eligible women in both rural and urban areas as a basic public health service since 2019. Based on this program, we conducted a prospective cluster randomized controlled screening trial in Shanghai, China.

Eligible women were aged 35–70 years without a history of breast cancer, including in-situ cancer or other cancers in the previous five years, without serious cardiopulmonary insufficiency, liver or kidney insufficiency or other systemic diseases, and with life expectancy of more than five years.

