### ***Randomization method***

Randomization was conducted by cluster, where districts rather than individuals were chosen as units of randomization. In order to avoid transfer between control and intervention cluster, urban levels were used as our strata. We then randomly selected one district out of seven urban areas as intervention cluster and another one out of nine suburban areas as control cluster.

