### ***Outcomes***

The primary endpoint of this study was to assess, and compare, the difference in the incidence of early breast cancer between two groups using different breast cancer screening methods (AI-assisted ultrasound screening/routine ultrasound screening). Early cancers should meet any of the following criteria at the time of diagnosis: less than 20 millimeters in diameter, no metastatic lymph nodes in the axilla, no distant metastasis, non-invasive cancers, stage 0, stage I, and stage IIA IIB (T2N1M0) breast cancer according to AJCC 8th staging.

The secondary aim was to determine the sensitivity, specificity, positive predictive value, and negative predictive value of the screening methods (AI-assisted ultrasound screening/routine ultrasound screening). Screening-detected cancers were defined as breast cancers positive for screening tests. We defined interval cancers as: breast cancers diagnosed after a negative screening test; breast cancers diagnosed after an indeterminate screening

test, but without any follow-up mammography or diagnostic examinations. A true-positive screening result was a positive result in a participant who was diagnosed with breast cancer by further diagnostic work-up. A false-positive screening result was a positive result in the absence of breast cancer. A true-negative screening result was a negative result in the absence of breast cancer and a false-negative test result was a negative result followed by diagnosis of interval cancer.

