#### ***Sample size calculation***

Sample size was primarily calculated by expected detection and incidence data from breast cancer. According to the positive detection rate of Asian women with suspicious breast cancer lesion (5/1000), 16,000 participants were required. Based on the reported data by Shanghai Center for Disease Control and Prevention in 2017, the age-specific incidence rate of breast cancer among women aged 35-69 in urban Shanghai was 125.75/100,000, so that 20 breast cancer cases were expected to be screened. Our previous breast cancer screening study showed that the early stage rate of screen-detected breast cancer reached 83%, predicting about 17 breast cancer at early stage would be diagnosed in this study. All this would meet the evaluation needs of endpoint indicators.

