#### ***Statistical analysis***

Numerical data were shown as means and standard deviation (SD) and categorical variables in percentages. Sensitivity was determined via dividing the numbers of true-positive screening by the numbers of true-positive and false-positive screening. Specificity was determined via dividing the numbers of true-negative screening by the numbers of true-negative and false-negative screening. To calculate 95% CIs, we did bootstrapping based on 5000 samples. The significance of the differences of incidences was assessed using Poisson regression. For categorical variables we used Fisher's exact test or likelihood-based  $\chi^2$  test.

All analyses were done with IBM SPSS (version 20).

This study was performed according to the guidelines of the Helsinki Declaration and was approved by the Medical Ethics Committee of Fudan University Shanghai Cancer Center (No. 2008223-22). Informed consent was obtained from all individual participants included in the study.

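### The Poisson comparison of incidence names no age term, although the arms are one urban and one suburban district and women span ages 35 to 70

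*Combined protocol and SAP*

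**What the plan says.** All references are to the combined protocol and SAP.

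- **Outcomes.** The primary endpoint concerns "the difference in the incidence of early breast cancer between two groups using different breast cancer screening methods".
- **Statistical analysis.** The matching method is "The significance of the differences of incidences was assessed using Poisson regression". The sentence gives no covariate, and no age standardisation or adjusted sensitivity analysis appears anywhere else. The section does not label this test as primary; the link is that it is the only method given for comparing incidence.
- **Randomization method.** The plan states that "districts rather than individuals were chosen as units of randomization", and that the selection took "one district out of seven urban areas as intervention cluster and another one out of nine suburban areas as control cluster".
- **Study population.** "Eligible women were aged 35–70 years without a history of breast cancer".
- **Sample size calculation.** The planning rate is itself restricted by age and place: "the age-specific incidence rate of breast cancer among women aged 35-69 in urban Shanghai was 125.75/100,000". No suburban rate and no age distribution by district is given.

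**The concern.** Randomisation balances age when many units are allocated. Here each arm is one district, and the urban or suburban character of the district is fixed by the arm. The age structure of the women screened in each arm is therefore whatever those two districts supply.

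A Poisson model with arm as its only term estimates the ratio of the two overall incidences. If incidence varies with age over a 35-year eligibility range and the two groups differ in age, that ratio mixes the screening method with the age mix, and the significance test cannot separate them. Age should already be on file for every woman, because eligibility depends on it, so this component can be removed by analysis. Most of the other differences between the two districts cannot.

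**Working it through.** **1. The plan's own event count.** Inputs from Sample size calculation: 16,000 women, 125.75 per 100,000, and an early-stage share of 83%.

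- Expected cancers: 16,000 × 125.75/100,000 = 20.12 (plan: 20).
- Expected early cancers: 20.12 × 0.83 = 16.7 (plan: about 17).

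Both figures reproduce.

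**2. Ratio with no true effect, from an age gap.** Assumptions, none of them in the documents: incidence changes by a constant proportion g per year of age; the two age distributions have the same shape and differ by d years in mean; the true ratio is 1. Then the crude ratio is (1 + g)^d.

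| g per year | d = 2 years | d = 5 years |
|---|---|---|
| 2% | 1.04 | 1.10 |
| 3% | 1.06 | 1.16 |
| 5% | 1.10 | 1.28 |

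These are for an older intervention district. If the control district is older, the reciprocals apply: 1/1.04 = 0.96 at one end and 1/1.28 = 0.78 at the other. With no age gap the ratio is 1.00.

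**3. Cross-check with two age bands.** Let R be the older-to-younger rate ratio, and let a and b be the shares of older women in the intervention and control arms. The crude ratio with no true effect is (1 − a + aR)/(1 − b + bR). Shares are centred on 50% (also assumed).

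- R = 1.5, a = 0.55, b = 0.45: 1.275/1.225 = 1.04.
- R = 3, a = 0.65, b = 0.35: 2.30/1.70 = 1.35.

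The range of 1.04 to 1.35 for age-mix gaps of 10 to 30 percentage points agrees in order of size with step 2. Adjusting for band returns 1.00 in each case.

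**4. Random error at the planned size.** Assume the 16.7 early cancers split equally between arms; the plan does not state the split.

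- SE of the log ratio: √(1/8.35 + 1/8.35) = √(4/16.7) = 0.49.
- 95% CI factor: exp(1.96 × 0.49) = 2.6.
- Largest bias in step 2: ln(1.28) = 0.25, and 0.25/0.49 is about half a standard error.

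**5. Effect on the test.** By normal approximation, null ratios of 1.10 and 1.28 raise a nominal 5% two-sided error to about 5.4% and 7.9%. In the two-band scenarios, summing Poisson probabilities for a Wald test, the rejection rate rises from 3.8% with no imbalance to at most 7.4%.

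**6. How many age terms the data can carry.** Five-year bands over 35 to 70 make seven groups, or 16.7/7 = 2.4 events each. Even with events spread evenly, the chance that at least one band has none is 1 − (1 − e^(−2.4))^7 = 49%.

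**The case against.** - **Silence is not a declaration.** A reader might infer that the plan commits to a crude analysis. The text does not say that; it names a model family and stops. What stands is that the covariates are unspecified. Fitting only what is written gives a ratio confounded by age, and fitting anything more leaves the choice of terms open until results are seen. Both readings call for the same edit.
- **The size is assumed.** This is correct. The documents give neither an age gap nor a gradient, and the planning incidence is one figure for ages 35 to 69, which shows no gradient within that range. The bias could be nil or could run in either direction. A reader might infer that it favours AI-assisted ultrasound; nothing in the documents supports a direction.
- **Random error is larger.** This also stands. With about 17 early cancers, the age effect is at most about half a standard error in step 2, so it would be wrong to infer that age would decide the result. It remains worth removing because it moves the point estimate, and more events would not shrink it.
- **Age is a small part of the problem.** Arm coincides with district, urban or suburban status, and operator type (primary health workers against hospital doctors, per Participants and intervention). Age adjustment touches none of these and supplies no between-district variance. This limits what the fix achieves, but does not argue against making it.

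**Conclusion.** The point holds as a gap in specification with a bias that can be avoided. The stated analysis includes nothing to account for age in a comparison of one urban with one suburban district. Under the assumed 2% to 5% per year and a gap of 2 to 5 years, the ratio with no true effect would lie at about 1.04 to 1.28, or 0.78 to 0.96 if the control district is older. Against a 95% interval that divides and multiplies the ratio by about 2.6 (equal split assumed), this is a modest shift that only slightly raises the false-positive rate.

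The tempting stronger conclusion is that age adjustment would make the arms comparable. The Randomization method section rules that out: with one district per arm, an age-adjusted ratio still cannot separate the screening method from the district.

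**What to change.** In the Statistical analysis section, specify the Poisson model for early breast cancer as arm plus one continuous, linear age term, and state the denominator. Do not use 5-year bands, given the sparse events. A single linear term removes the age effect fully only if log incidence is roughly linear in age, which is a reasonable compromise at about 17 events.

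Report the age-adjusted ratio first, with the crude ratio and the age distribution by arm as support. Participants and intervention describes the database as sealed in January 2024; if results have been seen, label the model as added after the plan.

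Add a sentence stating that age adjustment does not remove the differences that coincide with arm (district, urban or suburban status, operator type), and that the conclusion is limited by one cluster per arm.

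The cost is one model term, two lines of reporting and one limitation statement. No new data should be needed, provided age was recorded when eligibility was checked.
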